CI-5851-xxx (M Acoustic Earhook)	
 • This device should be used only by the individual for whom it is prescribed. • CHOKING HAZARD: Contains small parts that pose a hazard of inhalation, choking, or ingestion. If any parts are swallowed or inhaled, consult a physician or hospital immediately. • Do not leave children unattended with or allow children to play with the M Acoustic Earhook. • Do not allow children to place the M Acoustic Earhook in the mouth. • The M Acoustic Earhook should only be used by the intended recipient and not by any other individual. • Exposure of the M Acoustic Earhook to high humidity, sweat, or water could damage the speaker unit. • Placing the M Acoustic Earhook within close proximity to the headpiece magnet may damage the M Acoustic Earhook. • Remove your sound processor and consult your cochlear implant professional if uncomfortable sounds are heard or in case of discomfort, pain or skin irritation. • Do not use the M Acoustic Earhook unless the earwax protection is properly seated and the appropriate dome is attached. • In the unlikely event that the dome or earwax protection becomes dislodged in the ear canal, contact your cochlear implant professional. Do not try to remove the dome or earwax protection from your ear canal yourself. • If you observe any changes in sound quality with the M Acoustic Earhook, please contact Advanced Bionics or your cochlear implant professional. 
In the event that you experience any issues with your product, please contact your cochlear implant professional or the manufacturer. Do not attempt to service or modify the Naida CI or its accessories. Doing so may compromise system performance and will void the manufacturer's warranty. Products should be serviced only at Advanced Bionics and damaged products should be returned to Advanced Bionics.

Possible Adverse Events	

CI-5280 (Naída CI Q90 Sound Processors)
 
Undesirable side effects of Naída CI system may include skin irritation and discomfort from pressure on the ear, device overheating, or overly loud sounds. If any undesirable side effect is encountered, please remove your sound processor and consult your cochlear implant professional.
 
CI-5850 (Naída CI Q90 Acoustic Earhook)
 
Undesirable side effects of Naída CI system may include skin irritation and discomfort from pressure on the ear, device overheating, or overly loud sounds
 
CI-5293-xxx (Naída CI M90), CI-5295-xxx (Sky CI M90), CI-5851-xxx (M Acoustic Earhook)
 
Undesirable side effects of your Marvel CI sound processor and accessories may include skin irritation and discomfort from pressure on the ear, device overheating, or overly loud sounds. If any undesirable side effect is encountered, please remove your sound processor and consult your cochlear implant professional.
	
Claimed clinical benefit	

The intended clinical benefit of the Naída CI Sound Processor and Accessories as part of the HiRes™ Bionic Ear System is defined as:
 
 For adults: 
 Word recognition score in quiet higher or equal to 30% at a minimum of 12 months follow-up OR improvement higher than 30% compared to pre-operative stage AND/OR Sentence recognition score in quiet higher or equal to 40% at a minimum of 12 months follow-up OR improvement higher than 40% compared to pre-operative stage For children: 
 Before 4 years old: auditory awareness higher than 50% at a minimum of 12 months follow-up Above 4 years old: word/sentence recognition in quiet higher than 30% or improvement of 30% at a minimum of 12 months follow-up. 	
Expected lifetime	
CI-5280-xxx - Naída CI Q90	5 years
CI-5850-xxx - Naída CI Q90 Acoustic Earhook	1 year
CI-5293-xxx (Naída CI M90) CI-5295-xxx (Sky CI M90)	5 years
CI-5851-xxx (M Acoustic Earhook)	1 year
Invasiveness	
Non-invasive (external)	
Contact duration	
Intact skin, >30 days	
Type of use	

Single-use*	
Sterile	
Non-sterile	
Novel product	
	YES
x	NO
Novel related clinical procedure	
	YES
x	NO
Explanation of any novel features	
N/A	

*Single use as they do not fit the MDR (nor FDA) reprocessing definition of reusable devices. These devices are used on one individual during a single procedure corresponding to the lifetime of the devices.

4.5 Principle of Operation

The HiRes™ Bionic Ear System is a cochlear implant system designed to provide useful hearing to individuals with severe-to-profound hearing loss. It consists of internal and external components. Figure 4 illustrates the connections between CI components, including the fitting software. The cochlear implant (internal component), CPI fitting interface and fitting software are not under investigation but are included for completeness.

[figure not shown]

Figure 4 : Diagram of the connections between CI components

Figure 5 illustrates the auditory pathway with the cochlear implant and the behind-the ear sound processor. Sound is captured by microphones. Note: Advanced Bionics cochlear implants can receive sound from T-Mic, headpiece and processor microphones and auxiliary audio inputs sources.

1. The sound processor converts the captured sound into detailed digital information.

2. The processor sends power and digital information via the headpiece to the implant which is implanted under the skin.

3. The implant converts the digital information from the processor into electrical stimulation which is delivered to the auditory nerve through the electrode array. The auditory (hearing) nerve sends impulses to the brain where they are interpreted as sound.

[figure not shown]

Figure 5 : Auditory pathway of cochlear implant and BTE

4.6 Origin of development

The development of sound processor is based on addition and incrementation of new features to existing technologies. The Marvel sound processor is based on a previous generation of processor called Naída CI Q which is itself an improvement on the processor generation called Harmony. Electro-acoustic stimulation (EAS) was introduced with the Acoustic Earhook with the Naída CI Q sound processor.

4.7 Materials in contact with tissues

For each device under investigation, the materials in contact with tissues are listed in tables below (Table 5, Table 6, Table 7 and Table 8). Biocompatibility reports for each device and materials are available upon request.

Table 5 : Naída™ CI Q90 material specifications

Description	Raw Material	Colorants	Direct contact contact with human body
Case Top			Skin
Case Bottom			Skin
Program Button			Skin
Volume Rocker			Skin

Description	Raw Material	Colorants	Direct contact contact with human body
		SL	
Light Pipe		E	Skin
Acoustic Vent Mesh			Skin
Acoustic Vent Overmold			Skin
PIN 0.7 x 8.9mm			Skin
Earhook Locking Pin			Skin
PIN 0.7 x 6.7mm			No
P2i Coating (external)			Skin
Headpiece Connector			Skin
BTE Connector: Housing			Skin
BTE Connector: Detent Spring			Skin
Frame			No
PIN 0.7 x 7.15mm			No
PIN 0.7 x 5.4mm			No
Microphone Suspension (F)			No
Microphone Suspension (R)			No
Seal			No

Table 6 : Naída CI Q90 Acoustic Earhook material specifications

Description	Raw Material	Colorants	Direct contact or indirect contact with human body
Wire Jacket			Skin
Nozzle			Skin
Retention			Skin
Connector Body			Skin
Connector Socket			Skin
Housing Receiver			Skin
Housing Receiver Ink			Skin
Housing Receiver Ink			Skin
Housing Receiver Ink			Skin
Receiver			No
Receiver Cover Front			Skin
Receiver Cover Back			Skin
Epoxy Adhesive			Skin
CeruStop			Skin
Pin Removal Tool Body			Skin

Description	Raw Material	Colorants	Direct contact or indirect contact with human body
Pin Removal Tool Pin			Skin

Table 7 : Marvel CI sound processors material specifications

Description	Raw Material	Color	Direct contact contact with human body
Case Top, Case Bottom, Volume rocker			Yes, skin
Light Pipe			Yes, skin
Frame			No
Plate T-Mic Pins			No
Contact Pin			No
Suspension Microphone			No
Housing Connector BTE, Plate Locator BTE Connector			Yes
Battery Contact			No
Detent Spring			Yes, skin
Mic Retention Frame			No
Microphone cover			No
Mic Seal			No
Connector Seal			No
T-Coil Compression Suspension			No
Pin			No
Locking Pin			Yes, skin
P2i Coating (external)			Yes, skin

Table 8 : M Acoustic Earhook material and specifications

Description	Raw Material	Color	Direct contact contact with human body
Nozzle			Yes, skin
Connector			Yes, skin
Inner Mold			No
Wire Jacket			Yes, skin
Cover Back, Cover Front			Yes, skin
Retention			Yes, skin
O-Ring			Yes, skin
Housing Receiver			Yes, skin
Housing Receiver Ink			Yes, skin

4.8 Description traceability

This project includes retrospective analyses of clinical data. All devices were used in the clinical routine and tracked according to the appropriate regulations.

4.9 Summary of the necessary training

Personnel involved at the center are required to be familiar with the center's patient database and conventions for data coding and be able to extract data from it as well as compare data within it to e.g. ensure compliance with the inclusion criteria. Besides being familiar with this plan, no specific training is required.

5.0 Study Design and Justification

5.1 Description and justification for the design of the clinical investigation

This monocentric observational post-market clinical follow-up study (PMCF) of cochlear implants with Electro-Acoustic Stimulation is based on a retrospective data analysis of anonymized clinical data, in order to minimize risk and effort for the subjects. Reliable data to evaluate the efficacy of the Naída CI Q sound processor and the Naída CI M sound processor and their associated acoustic earhook, are already available in the form of data collected within the clinical routine. Analyses of these data do not have an influence on clinical routine and therefore do not impose any additional effort from the subjects.

A retrospective analysis of clinical data also minimizes the amount of data collected on each subject and consequently minimizes the risk of loss of personal data. To further protect subjects' data privacy, only anonymized data will be provided to AB.

5.2 Evaluation of the results of the relevant pre-clinical testing and prior clinical investigations

The Naída CI Q sound processor and the Naída CI M sound processor and associated acoustic earhook were qualified for long-term use in/on the human body through extensive preclinical testing using industry standards and specialized testing targeted for cochlear implants. This testing considered anticipated use case stresses which could affect the stability and reliability of the device, such as: impact, flexure and tensile stresses; body fluid/tissue contact; anticipated medical procedures for the patient and environmental elements.

The stability of the AB implants is assured by the materials and processes used in the manufacture of the devices. Reliable data to evaluate the efficacy of the HiRes Ultra CI HiFocus SlimJ implant and Naída CI Q sound processor and the Naída CI M sound processor and associated acoustic earhook are available in the form of data collected within the clinical routine. These data reflect real world evidence and are therefore suitable for PMCF objectives. Analyses of these data do not have an influence on clinical routine and do therefore not impose any additional effort on the subject.

5.3 Evaluation of relevant clinical data

The post market surveillance data including reliability, complaint, adverse events and Corrective Action Preventive Action (CAPA) data ensure that safety is consistently monitored. Once identified the events are thoroughly investigated, analyzed for root causes and the necessary actions taken to mitigate any risks.

The literature reviews performed examined all aspects of cochlear implantation clinical outcomes. These were conducted according to the state-of-the-art methodology and identified a large amount of published literature. The benefits underline the substantial benefits of cochlear implantation when applied to selected candidates having severe to profound sensorineural hearing loss.

These considerations indicate that the devices under evaluation have a positive risk/benefit profile and hence are suitable for clinical application. The data available from the risk analysis, the literature reviews, standards compliance, and data on long-term reliability all indicate that the products perform well in comparison to other cochlear implants and accessories that are already on the market.

5.4 Description of the clinical development stage

Not applicable, all devices under investigation are CE-marked.

5.5 Description of the measures taken to minimize or avoid bias, including randomization and blinding/masking

The cohort shall reflect the general population and represent real world data. The subjects are not selected, fulfillment of all inclusion criteria is the one condition. Factors such as gender or lifestyle are not expected to have an effect on study outcomes. By selecting all eligible subjects from the clinic's database in the analysis, selection bias is minimized.

5.6 Description of the specific medical or surgical procedures

There are no specific medical or surgical procedures included in this analysis. Cochlear implantation and follow-up of the subjects were performed according to the center's clinical routine.

5.7 Number of investigational devices

As this is a retrospective and observational clinical study, the number of devices under investigation corresponds to the number of included subjects. Bilateral patients received two devices. Therefore, the number of subjects is potentially lower than the number of devices.

This study will include all patients fulfilling inclusion and exclusion criteria and registered in the clinical patient database at the time of data extraction.

5.8 Description of the exposure to the investigational device

Investigational devices are CE marked and used according to their intended purpose as described in the IFU. Please, refer to section 4 for the description of the devices.

5.9 List of any other medical device or medication to be used during the clinical investigation

As this device is part of a system, the other medical devices used are the components of the cochlear implant, i.e., the compatible implant (HiRes Ultra and HiRes Ultra 3D with the SlimJ electrode in this study), headpieces and other accessories (connection cables, batteries) which are described above.

There is no additional medical device or medication involved as part of the study procedure.

5.10 Definition of completion of the clinical investigation

Not applicable, this a retrospective observational PMCF study for which data are already collected. This investigation will be considered completed when the report is finalized and all regulatory requirements are fulfilled, as applicable.

6.0 Objectives

6.1 Primary Efficacy Objective

The primary efficacy objective is to demonstrate that the group mean monosyllabic word recognition score with the EAS system in quiet at twelve months after first fitting is 30% or better. This efficacy outcome has been defined in accordance with the State-Of-The-Art (SOTA) performed by AB, and claimed clinical benefits for the HiRes Bionic Ear System from AB.

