1.0 Synopsis

Study Title	Retrospective analysis of long-term speech performance in cochlear implant recipients using electro-acoustic stimulation
Sponsor	Advanced Bionics AG
Investigational Device	Naída CI M and Naída CI Q and associated acoustic earhooks
Study Design	A monocentric observational post-market clinical follow-up study (PMCF) based on a retrospective data analysis of anonymized clinical data
Study Population	All subjects fulfilling inclusion and exclusion criteria and registered in clinical patient database at the time of the extraction of the data
Inclusion Criteria	Being implanted with Ultra or Ultra 3D SlimJ Being a user of the "acoustic earhook" system Having provided informed consent regarding use of his/her data for research
Exclusion Criteria	N/A
Primary Study/Efficacy Objective	Mean monosyllabic word recognition score with the EAS system in quiet at twelve months after first fitting of 30% or better
Primary Study/Efficacy Endpoint	Group average on the Freiburger Monosyllabic Word Test (in quiet) of 30% or more at twelve-month after first fitting
Secondary Study/Efficacy Objective	Mean sentence recognition score with the EAS system in quiet at twelve months after first fitting of 40% or better
Secondary Study/Efficacy Endpoint	Group average in the HSM sentence test (in quiet) of 40% or more at twelve-month after first fitting
Safety Objective	N/A
PMCF Objective (if required)	Collection of additional clinical data on acoustic earhook performance
Study Schedule & Duration	Estimated time for data collection, analysis and writing of the report: 3 months

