6.2 Secondary Efficacy Objective

The secondary efficacy objective is to demonstrate that the group mean sentence recognition score with the EAS system in quiet at twelve months after first fitting is 40% or better.

Subsidiary objectives include:

- Observation of the evolution of the mean monosyllabic word recognition score with the EAS system in quiet at 6, 12 months, 2, 3, 4 and 5 years after first fitting and more if available
- Observation of the evolution of the mean sentence recognition score with the EAS system in quiet at 6, 12 months, 2, 3, 4 and 5 years after first fitting and more if available
- Observation of the evolution of the mean sentence recognition score with the EAS system in noise at 6, 12 months, 2, 3, 4 and 5 years after first fitting and more if available.

There are no safety objectives for this clinical investigation. Safety events will not be collected retrospectively for the included subjects.

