8.2.3 Secondary efficacy hypothesis

The second efficacy hypothesis is based on the total number of subjects n and score (percentage of words correctly understood) in the HSM sentence test in quiet and in noise one year post activation.

Thus, the secondary efficacy hypothesis is:

$$\frac{\sum(HSM \text{ Score } 12 \text{ months})}{N} > 40\%$$

With:

HSM Score 12 months = % of correct sentence recognized at 12 months in quiet and in noise after the first fitting

N = number of datasets

- **Pass/fail criteria to be applied to the results of the clinical investigation**

The primary efficacy hypothesis needs to be fulfilled in order to consider this investigation successful.

- **Procedure for reporting any deviation(s) from the original statistical plan**

In case of a deviation from the statistical plan, the final report will highlight and justify the deviations.

- **Minimum and maximum number of subjects to be included for each center in multicenter clinical investigations**

This section is not applicable. The study is a monocentric study.

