12.2 Anticipated clinical benefits

The benefits will be the same for both Naída CI Q and Naída CI M sound processor recipients considering that the Acoustic Earhook for both sound processor are the same. The benefit of the study is the combined electrical and acoustic stimulation, which restores hearing in both silence and noise resulting in overall and hearing-specific improvement of quality of life.

The Intended Clinical Benefit of the sound processors and acoustic earhook as part of the HiResolution Bionic Ear System is to provide combined electrical and acoustic stimulation to restore hearing in silence and in noise when sound processors are enabled with the Acoustic Earhook.

The clinical benefits can be measured as follows:

For adults

- Word recognition score in quiet higher than or equal to 30% at a minimum of 12 months follow-up OR improvement higher than 30% compared to pre-operative stage.

AND/OR

- Sentence recognition score in quiet higher than or equal to 40% at a minimum of 12 months follow-up OR improvement higher than 40% compared to pre-operative stage.

For children:

Before 4 years old: auditory awareness higher than 50% at a minimum of 12 months follow-up.

Above 4 years old: word/sentence recognition in quiet higher than 30% or improvement of 30% at a minimum of 12 months follow-up.

12.3 Anticipated adverse device effects, residuals risks and possible interactions with concomitant medical treatments

The risks are similar for the two sound processors and associated acoustic earhooks under investigation. There are no specific risks related to the participation to this investigation as this is a retrospective observational data analysis in which data are already collected according to the center clinical care routine.

Residual risks and potential side-effects are listed in Table 4.

Users of the Naída CI Q & Naída CI M sound processors and associated acoustic earhook in the European Union should report any serious incident to their local competent authority and to Advanced Bionics.

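### A mean EAS score above 30% shows that earhook users reach the system-level bar; it cannot show what the acoustic earhook adds

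*Combined protocol and SAP*

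**What the plan says.** **Purpose.** The Synopsis gives the PMCF objective as "Collection of additional clinical data on acoustic earhook performance". Section 5.1 says that routine clinical data are adequate for judging the efficacy of the two processors and their earhooks. Table 3 (4.2) lists both earhooks among the devices under investigation, while 4.5 says the implant itself is not.

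**Bar.** The primary objective (6.1) is that the "group mean monosyllabic word recognition score with the EAS system in quiet at twelve months after first fitting is 30% or better". The secondary (6.2) is that the "group mean sentence recognition score with the EAS system in quiet at twelve months after first fitting is 40% or better". Section 6.1 bases the primary bar on the sponsor's state-of-the-art review and on the "claimed clinical benefits for the HiRes Bionic Ear System from AB". Table 4 introduces the thresholds with "The intended clinical benefit of the Naída CI Sound Processor and Accessories as part of the HiRes™ Bionic Ear System is defined as". Section 12.2 describes the benefit as "to provide combined electrical and acoustic stimulation to restore hearing in silence and in noise when sound processors are enabled with the Acoustic Earhook" and measures it by the same 30% and 40%.

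**Data.** Inclusion requires earhook use (7.1.3). Section 7.3.2 describes testing after implantation in one condition only, with the processor set as the recipient usually wears it. The extraction list in 14.3 contains post-fitting scores and no electric-only score.

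**Decision.** Section 8.2.3 states: "The primary efficacy hypothesis needs to be fulfilled in order to consider this investigation successful".

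**The concern.** The score being judged is produced by electric and acoustic hearing together. The bar is a fixed number claimed for the implant system without regard to the acoustic part, and no higher or incremental bar is set for EAS. Nothing in the planned data separates the two contributions.

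The stake is the conclusion. A report that meets the rule could be read as evidence that the earhook works, because the Synopsis and 5.1 name the earhook as a subject of evaluation and 8.2.3 labels the result a success. That reading would not follow from the data. Section 7.3.6, which lists what may compromise interpretation, mentions the single centre and the unverifiable source data but not this limit.

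**Working it through.** **Plan's own figures.** There is no alpha, SD, effect size or power calculation to reproduce. The expected 30 to 40 subjects (7.1.1, 8.2.1) is a headcount out of about 50 users: 30/50 = 60% to 40/50 = 80%.

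**Step 1: what the rule depends on.** Let E be the mean word score these recipients would reach with electric stimulation alone, and A the earhook's contribution in points. Neither is given. The observed mean estimates E + A, so under 8.2.2 the true mean meets the rule when E + A > 30, that is, A > 30 − E.

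| Assumed E (%) | Rule met when A exceeds |
|---|---|
| 25 | 30 − 25 = +5 |
| 30 | 30 − 30 = 0 |
| 40 | 30 − 40 = −10 |
| 50 | 30 − 50 = −20 |
| 60 | 30 − 60 = −30 |

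The inequality in 8.2.2 is strict, so at E = 40 a loss of exactly 10 points gives 30 and fails. Section 6.1, worded as 30% or better, would let it pass. A loss of anything less than 10, 20 or 30 points passes under both wordings.

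**Step 2: with sampling error.** P(pass) = Φ((E + A − 30) / (SD/√n)), with n = 30 to 40 from the plan and an assumed SD of 15 to 30 points. For E + A = 40:

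- n = 30, SD = 30: SE = 30/√30 = 5.48; 10/5.48 = 1.83; P = 0.966.
- n = 40, SD = 15: SE = 15/√40 = 2.37; 10/2.37 = 4.22; P > 0.999.

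| E + A | P(pass), n 30–40, SD 15–30 |
|---|---|
| 20 | <0.001 to 0.034 |
| 30 | 0.50 |
| 35 | 0.82 to 0.98 |
| 40 | 0.966 to >0.999 |
| 50 | >0.999 |

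The row E + A = 40 is reached by E = 40 with A = 0, by E = 50 with A = −10, and by E = 30 with A = +10. The pass probability is the same for a useless, a harmful and a helpful earhook. The secondary rule behaves alike: with E = 50, A = 0 and a bar of 40, P is 0.966 to 0.999 (n 30–40, SD 20–30).

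**Step 3: would any planned datum separate E from A?** No. There are no subjects without an earhook (7.1.3), no second test condition (7.3.2) and no electric-only column (14.3). Pre-operative scores, measured in routine care but not listed for transfer, would not help here: a change from baseline reflects implant and earhook together.

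**Step 4: what paired data could show.** If every one of the 30 to 40 subjects also had an earhook-off score, and the within-subject difference had an assumed SD of 10 to 20 points, the difference detectable with 80% power at two-sided 0.05 (noncentral t) would be 5.3 to 10.6 points at n = 30 and 4.5 to 9.1 at n = 40. With only 15 pairs it would be 7.8 to 15.6.

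**The case against.** The strongest reply is that the plan does not promise an earhook increment. Its objectives are worded for the EAS system, the need stated in 7.2.3 is for performance data in EAS users, and the Synopsis speaks of collecting data. Section 12.2 adopts the 30% and 40% thresholds for the processor with the earhook enabled, so the bar is not merely borrowed. A fixed performance threshold is a legitimate choice for a single-arm retrospective PMCF study. All of this stands, and it means that a pass is informative about the EAS system. It does not support an efficacy conclusion for the earhook, which the wording of the Synopsis and 5.1 leaves open.

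A reader might go further in three ways that the documents do not support:

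- *That electric-only recipients must reach the same bar.* Table 4 offers adults "Word recognition score in quiet higher or equal to 30% at a minimum of 12 months follow-up OR improvement higher than 30"% over the pre-operative stage, joined by and/or to a sentence criterion, and gives children other criteria. No section requires each recipient to reach 30% or 40%.
- *That a pass says nothing about the earhook.* It says how earhook users score; it is silent on what the earhook adds.
- *That the earhook is probably useless or harmful.* Nothing suggests this. The negative values of A above only show what the rule tolerates.

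Two limits remain. The state-of-the-art review cited in 6.1 is not among the documents, so any EAS-specific support in it cannot be checked. Earhook-off scores may not exist, since 7.3.2 and Table 9 describe no such test.

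**Conclusion.** The point holds as a limit on interpretation. Meeting the rule shows that earhook users, as a group, reach the system-level threshold with electric and acoustic stimulation combined. It cannot show the earhook's efficacy or added benefit.

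That the two contributions cannot be separated follows from the design and needs no numerical assumption. The size does: how easily the rule is met without any earhook effect depends on E, for which 40, 50 and 60% are illustrations. With E at 30% or below, a true mean above the bar would imply a positive effect, but E is not measured, so the report could not claim to be in that case. The design need not be rebuilt. The stated conclusion should be narrowed before the data are analysed.

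**What to change.** 1. In 6.1 and in the pass/fail text of 8.2.3, state that meeting the bar shows performance of the EAS system in earhook users and does not show the efficacy or added benefit of the acoustic earhook. Align the PMCF objective in the Synopsis and the efficacy sentence in 5.1, and list the limit in 7.3.6. The cost is wording only, and a narrower claim.

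2. Add to the 14.3 extraction any earhook-off word and HSM scores already recorded for the same ear at the same visit. Where they exist, report the paired EAS minus electric-only difference with a 95% confidence interval and the number of available pairs, labelled descriptive. The cost is extra columns in the same export, with no new patient procedures. The pairs may be few, absent or selected, for instance if only some recipients were tested both ways, and the report should say so.

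I would not add a cohort of SlimJ recipients without an earhook. It lies outside the inclusion criteria in 7.1.3, would need a formal amendment under 16.1, and would be confounded by residual hearing, so it would not isolate the acoustic contribution either.
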